Outcomes from a Mobile Smoking Cessation Program During a Monitoring Period of 6 Months

Issue Date: September 29, 2017

Prepared By:	
Sr. Director, Clinical and Medical Affairs, Carrot Inc.	
Approved By:	
	_
President and CEO, Carrot Inc.	
	_
Regulatory Affairs, Carrot Inc.	
VP, Behavioral Science, Carrot Inc.	
Director, Clinical Affairs, Carrot Inc.	

Protocol Summary

Device Names	Carbon Monoxide Breath Sensor System (COBSS) and Pivot App		
Protocol Title	Outcomes from a Mobile Smoking Cessation Program During a Monitoring Period of 6 Months		
Principal Investigators			
Protocol Number			
Protocol Version			
Protocol Shorten Name	6-Month Outcomes of a Mobile Smoking Cessation Program		
Study Design	Prospective, open label, single center clinical study enrolling up to 310 subjects (up to 50 run-in subjects, and 260 general subjects) No medical decisions will be made related to test results.		
Objective	We aim to assess a mobile smoking cessation program delivered through the Pivot Application ('App'). We will evaluate user engagement and retention in the program, attitude towards smoking and smoking behavior, quit rates, relapse rates, and quality of life over the study period, as well as user feedback on the program.		
Potential Subjects	Up to 310 subjects who report daily smoking behavior (smokers).		
Inclusion Criteria	 18-65 years of age English speaking Smokes daily Smokes 5 or more cigarettes per day Owns and uses a smartphone (iPhone 5 and above, operating system iOS 9.0 and above, or, Android 4.4 and above, operating system Android 4.4 and above) Employed at least 20 hours per week Lives in the USA Understands and willing to sign the Informed Consent Form 		

Recruitment Potential subjects will be identified via advertisement at outdoor locations (i.e. flea markets, outside of movie theaters, shopping malls, train stations, stores that sell cigarettes), print media (i.e., local newspapers, billboards), web media (i.e., Craigslist, Facebook, Survey Monkey, Instagram, Twitter, Google Ads, Reddit, smokefree.gov) and through clinical research recruiters. Study Session Potential participants will complete an online screening form. Eligible participants will be called to confirm eligibility, discuss the study, and have their questions about the study answered. Interested eligible participants will then be emailed the registration link, which includes the electronic informed consent. After providing electronic informed consent, subjects register online and receive the COBSS device. Baseline questionnaires (demographics, smoking history, and attitude towards smoking) are completed, and subjects then self-train to use the COBSS (which includes the CO Breath Sensor and Breath Sensor App, or BSA) and the Pivot App. The BSA is required for the breath sensor to communicate with the subject's smartphone and allows basic viewing of CO sample values. The Pivot App comprises 5 sequential phases (Explore, Build, Mobilize, Quit and Secure). The Pivot App provides the user with information about CO sample values and CO trends, as well as the ability to log cigarette events (when subject smokes), view cigarette consumption trends, view instructional videos, complete educational activities and challenges, and engage with a coach. During the registration process, subjects are paired with a live coach who will provide support using in-app text messaging during the study. During the study, subjects log their cigarette events in the Pivot App and submit breath samples using the CO Breath Sensor. They also complete short (2-8 minutes) activities in the Pivot App, create a quit plan, and periodically engage with their coach. The primary phase of the study, during which participants are using the Pivot program, is 14.5 to 18.5 weeks in duration, depending on participant relapse/exit/re-entry rates and navigation of the phases of the Pivot App journey (Build is self-guided and lasts 1-28 days). Three months after completing the primary phase of the study, participants are asked to complete a final exit questionnaire. Questionnaires assessing smoking behavior, attitude towards smoking, quality of life, engagement with the program and feedback on the program are conducted at baseline, at the end of each Pivot App phase and at 3 months after completing the primary phase of the study. In addition, more detailed user

feedback on the experience is sought upon completion of the Secure phase of the Pivot App, or upon the end of the participant's engagement with the app, whichever occurs first. Upon return of the study device and completion of the questionnaire conducted 3 months after completing the primary phase of the

study, the study is considered complete.

Endpoint and analysis

We will compare the following variables at entry, after completion of each Pivot App phase, and/or at exit.

Engagement:

- Weeks of active engagement
- Phase completion
- Number of app opens

Smoking Behavior:

- Number of cigarettes smoked per day
- Quit attempts
- Quit rates: 7-day, 30-day point prevalence
- Sustained quit (continuous days quit)
- Smoking reduction (in participants who do not quit)

Responses to questionnaires:

- Measurements assessing attitude toward smoking
 - Readiness to quit
 - o Goals related to smoking behavior
 - Confidence to quit
 - o Difficulty maintaining quit
- Net Promoter Score (NPS)
- NPS, Coaching
- Nicotine Dependence
- Quality of Life

Schedule of Study Activities

	Screening	Day 0	Day 1	Pivot App - Explore (9 days)	Pivot App - Build (1 - 28 days)	Pivot App - Mobilize (7 days)	Pivot App - Quit (7 days)	Pivot App - Secure (11 weeks)	Exit - 3 mos after Secure or 3 mos after the end of participant's engagement with the app
Eligibility Confirmed	Х								
Informed Consent		Х							
Baseline Questions (demographics, thoughts about smoking)		Х	Х	х					
Receive COBSS*			Х						
Cigarette Logging**				Х	Х	Х	Х	Х	
Breath Sampling***				Х	Х	X	Х	Х	
Coach-Initiated Interactions				Х	Х	X	Х	Х	
Questionnaire			Х	Х	X	х	Х	Х	Х
Questionnaire (thoughts about smoking and the experience of using the device)								Х	
Exit questionnaire									Х
Return Breath Sensor									X
Study Completion									Х

^{*} COBSS received by participant only after confirmation of eligibility and provision of informed consent

^{**} Cigarette logging should stop at the beginning of the Quit phase of the Pivot App (assuming participant quits smoking), however, participants are asked to log all cigarettes, including those that occur during a lapse or relapse

^{***} Suggested breath sampling schedule varies from one phase to the next

Table of Contents

1		In	roduction 9		
	1.1		Background		9
	1.2		Study Rationale		10
	1.3		Potential Risks a	and Benefits	10
	1	.3.	1 Known Pot	tential Risks	10
	1	.3.	2 Known Pot	tential Benefits	10
	1	.3.	Risk Benef	fit Assessment	10
2		St	udy Objective		11

1.1 Background

The smoking of tobacco products is a leading cause of preventable morbidity and mortality, excess health care expenditure, and lost work productivity.

We have developed a personal mobile CO breath sensor (study device, Carrot Sense) that communicates with a mobile app (BSA) on a smartphone to display the results to the user. The BSA is required for the breath sensor to communicate with the subject's smartphone and allows basic viewing of CO sample values. In addition, we have developed the Pivot App, which provides additional information about CO sample values and CO trends, as well as the ability to log cigarette events (when subject smokes), view cigarette consumption trends, complete educational modules and challenges, view instructional videos, create a quit plan, and interact with one's coach. Enabling a smoker to monitor and track the level of CO in their breath, while

logging the times of the cigarette consumption and participating in an educational program with coaching may lead to attitude changes, quit attempts, and/or smoking cessation.

This study aims to assess changes in smoker's behavior and attitudes toward smoking during and after using the Pivot mobile smoking cessation program.

1.2 Study Rationale

We will assess engagement, motivation, smoking behavior changes, nicotine dependence, smoking cessation rates, quality of life, retention and general feedback in smokers using the Pivot mobile smoking cessation program over a period of 3 months, with 3-month follow-up after program completion.

1.3 Potential Risks and Benefits

1.3.1 Known Potential Risks

There are no anticipated risks or harms to the subject. No medical decisions are made based on study data.

1.3.2 Known Potential Benefits

It is possible that some subjects may experience an increased awareness of their smoking behavior, decrease their smoking, or quit smoking altogether.

1.3.3 Risk Benefit Assessment

Given the non-invasive nature of the breath sampling and the data collection, there are no anticipated risks to subject safety. This study assesses a mobile smoking cessation program, which may help subjects decrease or quit smoking. No medical decisions are made based on study data.

2 Study Objective

We aim to assess the Pivot mobile smoking cessation program. We will assess participant engagement with and feedback of the program, as well as changes in attitude towards smoking and smoking behavior over the study period.

3 Device Descriptions

3.1 Carbon Monoxide Breath Sensor System (COBSS)

The Carbon Monoxide (CO) Breath Sensor System (COBSS) comprises a personal mobile breath sensor (CO Breath Sensor) capable of measuring the level of CO in exhaled breath and an app for smartphones which displays the exhaled breath CO value to the user.

3.1.1 CO Breath Sensor

The CO Breath Sensor (Figure 1) is portable, battery-powered, and small enough to be conveniently carried by the user throughout the day (pocket, purse, backpack). The CO Breath Sensor is rechargeable using a micro-USB cable. The LED pulses orange while charging and then solid green when fully charged.

The CO Breath Sensor pairs to the app (BSA) on the smartphone via low-energy Bluetooth. The user submits a breath sample by exhaling (blowing) into the CO Breath Sensor via a provided straw (polypropylene, reusable, cleaned with soap and water, replaced as necessary). In the study, a pack of 7 straws is provided with the CO Breath Sensor.

Figure 1. CO Breath Sensor

Figure 2. BSA CO Log

3.1.2 Breath Sensor App

The Breath Sensor App (BSA) for smartphones is required for the breath sensor to communicate with the subject's smartphone and allows basic viewing of CO sample values. The CO breath sample values are presented in parts per million (ppm) within color coded bars (see Figure 2). A low level in a smoker (CO value of 0-6 ppm, Green) does not mean it is safe to smoke. Likewise, a non-smoker may have CO levels higher than 6 ppm (Orange or Red) due to environmental exposure. These ranges are derived from many clinical studies using point measurements at various times of the day ______. Should the subject submit a breath sample using improper technique, s/he will receive an error message in the CO Log.

The results in the app are stored in a secured database. Study personnel will be able to view these results as well as activity in the app.

The app has features to allow the subject to set reminders, vibration, volume, and other preferences.

3.2 Pivot App

Participants use the Pivot App as the main focus for study interactions. In the Pivot App, participants may perform the following main actions:

- View CO sample values, CO load, and CO trends
- Log cigarettes and see the associated data including cigarette trends
- Complete educational activities
- Complete challenges and practice quits related to the educational activities
- Set a Quit date, then build and revise the Quit Plan
- Read back all information entered in "My Story"
- In-app chat with the Pivot coach

More specifically, participants can see their individual CO sample values in the CO Log (as with BSA), and can also view CO load (area under the curve for CO exposure over 24 hours) and CO load trend day to day. Participants can also log cigarettes, view number of cigarettes smoked per day and trends in cigarette consumption. The participant's location at time of cigarette logging will be collected if the participant opts in for this feature.

In addition, activities are delivered and completed in the Pivot App. These are educational activities designed to increase participant's awareness of smoking risks and raise questions about the role of smoking in the participant's life. Some of these activities are combined with "challenges" that the participant can choose to accept or defer, which ask the participant to take particular actions related to the educational activity. These actions can range from thinking about a particular way smoking affects their life to attempting to replace smoking a cigarette with another activity of their choosing. Coaching provides human support and guidance, and is conducted via in-app chat in the Pivot App.

4 Study Design and Overview

4.1 Study Design

CONFIDENTIAL

,
This is a prospective open-label clinical trial conducted with IRB approval in up to 310 subjects who report daily smoking (up to 50 run-in subjects, and 260 general subjects). Potential
subjects will be recruited and prescreened as described in section 4.4
Potential participants will complete the Online Screening Form
Screening Form submission will be reviewed by study staff. Eligible participants and those of
uncertain eligibility (ex. potential participant's Online Screening Form was incomplete) will be
contacted by phone by study staff or the clinical recruiter to confirm eligibility, provide more
details about the study, and answer any questions the potential participant may have.
Eligible potential participants who remain interested in participation will be emailed the web
registration link. This link, along with the phone call that occurred previously, will be used to
verify the potential participant's identity. During the identity verification portion of the online
registration process, the potential participant enters contact information and verifies their identit
through a link sent to the email address they provide
Every online submission from a potential participant will be reviewed by study staff and any
discrepancies will be addressed through a phone call and/or possible videoconference with the
potential participant (for example, more than one online submission with the same name,
address, email address or phone number). Should a videoconference be pursued, such
communication will occur in a private office setting with only necessary study staff present and
the privacy of the potential participant protected (office door closed; screen not visible to anyone
other than necessary study staff; headphones used if possible, if not possible, volume at the
lowest level that allows for coherent dialogue).
After verification of eligibility and identity, potential participants will be asked to provide informed
consent. Potential participants will have the opportunity to ask questions of the study
investigator team during the informed consent process. Those who agree to participate will electronically sign the informed consent form
Study staff must review the eligibility and identity criteria, document the resolution of any
discrepancies from the identity verification process, answer any questions during the informed
consent process, and confirm informed consent is signed before approving a participant for
entry.
Upon approval for entry, study participants receive the study device. Upon receipt of the study
device, participants will download the apps on their smartphone and use device labeling (User
Manual Reference Card
Insert Card Barrier , Box Sleeve Label Label) to set up and self-train on the
device and apps.
Participants will have access to Customer Service and study staff as well if they need additiona
support. Participants are provided the study instructions during the online registration process:

Carrot Inc. 6-Month Outcomes of a Mobile Smoking Cessation Program Ver B

the Pivot mobile smoking cessation program consists of 5 phases (Explore, Build, Mobilize, Quit, and Secure); during the study, participants provide breath samples using the CO Breath Sensor, log cigarettes in the Pivot app, complete daily activities in the Pivot App, and engage in coach-initiated interactions conducted through in-app text.

Study participants will be asked to complete questionnaires (in-app and through email) at baseline, after each phase, and at exit. In addition, more detailed user feedback on the experience is sought upon completion of the Secure phase of the Pivot App, or upon the end of the participant's engagement with the app, whichever occurs first. Upon return of the study device and completion of the exit questionnaire (conducted 3 months after completing the primary phase of the study), the study is considered complete.

4.2 Study Endpoint

Primary endpoint:

- Phase completion of those who started a phase, the proportion who completed that phase, assessed for each phase of the Pivot program.
 - Phase completion is defined as completing the last in-app activity from that phase
 - Exception: completion of Secure is defined as being in Secure for 11 weeks, and having engaged with the program at least once within Secure (app open, daily check-in, responds to coach, logs cig), and providing smoking status (cigarettes per day and 7-day point prevalence) in the end-of-Secure questionnaire

Additional endpoints include:

Engagement:

- Weeks of active engagement
- Number of app opens
- Phase completion proportion of intention to treat (ITT) cohort that completes each phase
 - ITT cohort comprises participants who signed informed consent and completed onboarding in the Pivot app (i.e. downloaded the BSA and Pivot apps, completed device set-up, and completed the three guided breath tests, or GBTs)
- Program completion proportion of intention to treat (ITT) cohort who have been in Secure for 11 weeks and have engaged with the program at least once (open app, or complete a daily check-in, or respond to coach, or log a cigarette), and, provides smoking status (cigarettes per day and 7-day point prevalence) in end-of-Secure Survey

Smoking Behavior:

- Number of cigarettes smoked per day
- Quit attempts (participant did not smoke for at least 24 hours)
- Quit rates: 7-day, 30-day point prevalence

CONFIDENTIAL

- Assessed in the ITT cohort
- Assessed in the Per Protocol cohort (individuals who complete the end-of-phase survey in the phase during which the question is being asked or, complete the exit survey at the end of their engagement with the app, whichever occurs first)
- Sustained quit (continuous days quit)
 - Assessed in the ITT cohort
 - Assessed in the Per Protocol cohort
- Smoking reduction (in participants who do not quit smoking) proportion who achieved 50% cigarettes per day (CPD) reduction or more at study exit

Responses to questionnaires:

- Measurements assessing attitude toward smoking
 - o Readiness to quit
 - Goals related to smoking behavior
 - Confidence to quit
 - o Difficulty maintaining quit
- Net Promoter Score (NPS)
- NPS, for coaching
- Nicotine Dependence
- · Quality of Life

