Suggested breath CO sampling protocol	 2 days of "intensive" sampling (hourly) to benchmark – beginning and end of Mobilize Remaining days in between are 3 breaths a day: morning, mid-day, evening 			
Coaching frequency	 Intro touch point to Mobilize with two interactions on completion of specific activities that prepare users for quit day. Wrap-up touch point to review quit plan If a user has not completed activities, milestones and/or has not had a coaching interaction within the past 2 days, the coach will reach out to the user to check in. 			
Study management	If participant does not use the app at least once in 7 days (no cig logging, or CO sampling, or start/complete activity, or start/complete challenge, or complete daily check-in, or respond to coach outreach), study staff will email on day 9, text on day 10, call on day 11, and call on day 13			

Quit				
Duration, pace, key components	 7 days from quit date, time based, activities are unlocked daily Daily check-in introduced Red 'guy' on Pivot app dashboard turns green, Crush-a-Craving button added 			
Intent	 Getting through the toughest week Lapse and relapse handling 			
Activity/content	 Daily check-in, must be completed to access rest of app One activity is unlocked per 24h 			
Cigarette logging	Daily check-in asks if user smoked previous day, if so, then directs them to log cig			
Suggested breath CO sampling protocol	 Encourage light use to see progress 3 breaths a day, morning, mid-day, evening Plus every time user has a craving 			
Coaching frequency	 Intro touch point to Quit with two strategic interactions after completion of smoke-free milestones (Quit: 24 hours and 72 hours) Wrap-up touch point to review progress, celebrate smoke-free milestones and identify areas of the quit plan that may need to be adjusted going forward – guide to move to Secure. If a user has not completed activities, milestones and/or has not had a coaching interaction within the past 2 days, the coach will reach out to the user to check in. 			
Study management	If participant does not use the app at least once in 7 days (no cig logging, or CO sampling, or start/complete activity, or start/complete challenge, or complete daily check-in, or respond to coach outreach), study staff will email on day 9, text on day 10, call on day 11, and call on day 13			

	Secure
Duration, pace, key components	11 weeks from quit dateDaily check-in
Intent	Lapse and relapse handling
Activity/content	Daily check-in with journaling

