Cigarette logging	Daily check-in asks if user smoked previous day, if so, then directs them to log cig.
Suggested breath CO sampling protocol	No explicit sensor use schedule, but sensor is incorporated as follows: • Encourage people who find the 3 times a day useful to keep doing that. • Allow users to set their own milestones, some can be sensor related. Pivot app also gives trophies for breath samples associated with abstinence to augment this. "Take a breath samples to celebrate your smoke-free success."
Coaching frequency	 3-4 coach-initiated interactions per week for the first 3 weeks For users who achieve 30day PP at 3 weeks or 7 weeks in Secure, coaching frequency drops to once weekly, until/unless user indicates lapse or relapse.
Study management	 For the first 3 weeks: If participant does not use the app at least once in 7 days (no cig logging, or CO sampling, or start/complete activity, or start/complete challenge, or complete daily check-in, or respond to coach outreach), study staff will email on day 9, text on day 10, call on day 12, and call on day 14 For the remaining 7 weeks: If participant does not use the app at least once in 14 days (no cig logging, or CO sampling, or start/complete activity, or start/complete challenge, or complete daily check-in, or respond to coach outreach), study staff will email on day 16, text on day 17, call on day 19, and call on day 21

The following table details the different questions being asked of participants at specific time points over the course of the study.

		1	1	1	T	I	I	1	1	T
	Baseline	Explore	Build	Mobilize	Quit (1wk)	Secure - 1wk (2wk post Quit)	Secure - 3wk (1mo post Quit)	Secure - 7wk (2mo post Quit)	Secure - End (3mo post Quit)	Follow -up (6mo)
Cigarettes per day	х	Х	Х	х	х	Х	Х	Х	х	х
Tobacco Forms Used	Х		Х		Х		х	Х	Х	Х
Readiness to Quit (1-10)	х	Х	Х	Х						
Success, if were to quit (1-10)	х	х	Х	Х						
Difficulty staying quit, (1-10)	Х	Х	Х	Х						
Quitting Goal	х	Х	Х	х						
Nicotine Dependence		Х		Х						
7day Point Prevalence					х	х	х	Х	Х	х
30day Point Prevalence							х	Х	Х	х
Date of Last Cig					Х	Х	Х	Х	х	Х
Longest Smoke- free Interval					Х	X	X	Х	Х	Х
Quit Attempts					Х	Х	Х	Х	х	Х
NPS		Х	Х	Х	Х				х	
Coach NPS		X	Х	Х	Х				Х	
Quality of Life	Х								Х	Х
Cessation Medications	х			Х	х	×	×	Х		Х

Participants will receive an email, text or phone call from study staff to inform them they have a questionnaire to complete (

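### The Secure table in Section 5.3 leaves 10 weeks in Secure where the primary endpoint needs 11, and Program completion omits the within-Secure condition (minor)

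*Combined protocol and SAP*

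**What the plan says.** Section 4.2 defines the primary endpoint as the proportion of those starting a phase who complete it. Four phases are completed by finishing the last in-app activity. Secure is a stated exception: "completion of Secure is defined as being in Secure for 11 weeks, and having engaged with the program at least once within Secure", together with cigarettes per day and 7-day point prevalence reported in the end-of-Secure questionnaire.

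Among the additional endpoints, Program completion is the proportion of the ITT cohort "who have been in Secure for 11 weeks and have engaged with the program at least once (open app" and other listed actions), again with smoking status reported. The engagement clause here is not limited to the Secure phase.

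Several places bear on how long Secure lasts:

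- Schedule of Study Activities, column header: "Pivot App - Secure (11 weeks".
- Protocol Summary, on the primary phase of the study: it "is 14.5 to 18.5 weeks in duration".
- Section 5.3, Quit table: "7 days from quit date, time based".
- Section 5.3, Secure table, duration row: eleven weeks, counted from the quit date.
- Section 5.3, Secure table, study management row: one inactivity rule for the first 3 weeks, and a second that begins "For the remaining 7 weeks".
- Section 5.3, questionnaire table, last in-program column: "Secure - End (3mo post Quit".

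**The concern.** Section 5.3 is the text that staff would use to run the program. If its Secure table is followed to the letter, a participant leaves Secure after 10 weeks and cannot satisfy a primary-endpoint component that asks for 11. If the end-of-Secure questionnaire were tied to that same point, its quit rates would also be taken a week early. If Secure instead runs for 11 weeks, the inactivity rules as written stop one week before it ends.

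The second matter is a mismatch between two definitions that look alike. Section 4.2 also reports phase completion in the ITT cohort. For Secure, that proportion has the same denominator as Program completion and, apart from the within-Secure condition, the same numerator. The two figures should agree, but as worded they can differ.

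**Working it through.** **1. Secure length implied by the Secure table.** Inputs: eleven weeks from the quit date (Secure table), Quit occupying the first 7 days from the quit date (Quit table), and phases taken in sequence (opening text of Section 5.3).

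- Days left for Secure = 11 × 7 − 7 = 70 days = 10 weeks.
- Outreach periods = 3 + 7 = 10 weeks.
- Endpoint requirement = 11 × 7 = 77 days.

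The table does not print a 10-week figure; two of its rows imply it.

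**2. The plan's own duration, reproduced.** Primary phase = Explore 9 days + Build 1 to 28 days + Mobilize 7 days + Quit 7 days + Secure.

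| Secure length | Shortest | Longest | Gap from 14.5 / 18.5 weeks |
|---|---|---|---|
| 77 days | 9+1+7+7+77 = 101 d = 14.43 wk | 9+28+7+7+77 = 128 d = 18.29 wk | 0.07 / 0.21 wk |
| 70 days | 9+1+7+7+70 = 94 d = 13.43 wk | 9+28+7+7+70 = 121 d = 17.29 wk | 1.07 / 1.21 wk |

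Adding one entry day gives 14.57 to 18.43 weeks with 77 days, and 13.57 to 17.43 weeks with 70. Only the 11-week Secure reproduces the stated range.

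**3. Questionnaire labels.** Take Secure to start on day 7 after the quit date.

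| Column | Day after quit date | Label |
|---|---|---|
| Secure 1 wk | 7 + 7 = 14 | 2 weeks |
| Secure 3 wk | 7 + 21 = 28 | 1 month |
| Secure 7 wk | 7 + 49 = 56 | 2 months |
| Secure end, 11 weeks | 7 + 77 = 84 = 3 × 28 | 3 months |

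The labels follow four-week months and fit 11 weeks. With 10 weeks the last column would fall on day 7 + 70 = 77.

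**4. What the short outreach period affects.** The later rule triggers after 14 idle days, with contacts on idle days 16, 17, 19 and 21. Assume that a rule triggered by Secure day 70 is carried through.

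- Last use on day 56: trigger on day 56 + 14 = 70; contacts on days 72, 73, 75 and 77. Nothing is lost.
- Last use on day 57: trigger on day 71, outside the stated period. Contacts on days 73, 74 and 76 are lost within Secure; the fourth (day 78) would fall after Secure in any case.
- Last use on day 61: first contact on day 61 + 16 = 77, the last day of Secure.
- Last use on day 62 or later: first contact on day 78 or later, so an eighth week adds no contact within Secure.

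The slip therefore affects last-use dates of Secure days 57 to 61. If instead all contacts were cut off at day 70, contacts would be lost for last use after day 70 − 21 = 49.

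**5. Program completion.** The ITT cohort consists of people who consented and completed onboarding in the Pivot app, including three guided breath tests (Sections 4.2 and 5.2). They have opened the app, and an app open counts as engagement. With no phase limit, the clause excludes nobody. The two definitions part only for someone with 11 weeks in Secure, no engagement during Secure, and smoking status supplied outside the app. Section 4.1 leaves this open, since participants are "asked to complete questionnaires (in-app and through email) at baseline, after each phase, and at exit". It does not say which questionnaires use which route.

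**The case against.** The strongest reply is that nobody would be misled. The schedule, the endpoint, the duration and the questionnaire labels all point to 11 weeks in Secure, and the Revision B entry in Section 9 names a Secure 11-week questionnaire. The duration row may be loose wording for the end of Quit, and the word *remaining* in the outreach row naturally means the rest of the phase, whatever the numeral. This largely stands. It makes early closure of Secure, or early measurement of quit rates, unlikely. It does not remove the conflict, because two rows of the operational table lead separately to 10 weeks.

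A reader might infer that the last week of Secure has no contact just before the questionnaire that decides completion. The documents do not support that. Section 5.3 has staff notify participants by email, text or phone when a questionnaire is due, Section 6.3 has the team seek completion of data forms, and outreach triggered by day 70 would run on to day 77.

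On Program completion, the reply is that context makes the intended meaning plain. That is fair, and it is why the matter is editorial. If the broader wording was deliberate, the clause does nothing and could be deleted.

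**Conclusion.** The conflict is real and minor. The Secure table implies 70 days in Secure and an end at day 77 after the quit date; the endpoint and the supporting text imply 77 days and day 84. The endpoint is right and the table needs correcting. The outreach shortfall concerns only participants whose last use falls late in Secure, after about day 56. The Program completion wording can count someone whom the primary Secure definition excludes, probably in few cases. The documents give no engagement or response rates, so neither effect on a completion proportion can be sized.

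This rests on the phases running in sequence, on Secure starting 7 days after the quit date, and on triggered outreach being carried through.

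Two stronger readings are tempting. A reader might infer that the Secure rule is defective because one app open meets its engagement clause. The rule is an explicit, prespecified exception that also requires 11 weeks in the phase and reported smoking status, and app opens and weeks of active engagement are endpoints in their own right. A reader might also infer a contradiction between the two-week absence allowance in Section 5.3 and the 11-week clock. The plan does not link the two, so no contradiction is shown.

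**What to change.** Three wording changes:

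- Section 5.3, Secure table, duration row: *11 weeks from the end of Quit (12 weeks from quit date)*.
- Section 5.3, Secure table, study management row: *remaining 8 weeks*, so that 3 + 8 = 11.
- Section 4.2, Program completion: insert *within Secure* after the requirement to have engaged at least once.

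The primary endpoint definition stays as it is. No new data or analysis is needed. The cost is a short protocol edit and, for late inactivity, a few more staff contacts. Once corrected, Program completion equals the ITT completion proportion for Secure, so the two can be reported as one figure.
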